**FORM: Application for Human Research**

| NUMBER | FORM DATE | PAGE |
|--------|-----------|----------|
| F200 | 02/2014 | 16 of 44 |

443 burdensome than it appears, as over 30 participants have already successfully completed this same
444 protocol in our pilot study of mild traumatic brain injury without any complaints or discontinuations due
445 to excessive burden. Finally, the **potential impact** of this study is high because of the capability of
446 transitioning the research to direct clinical application almost immediately. If the BL treatment is
447 demonstrated as effective, this approach would be readily available for nearly immediate large-scale
448 implementation, as the devices have been widely used for years in other contexts, are already safety
449 tested, and commercially available from several manufacturers for a very low cost. Thus, the impact of
450 this research on treating PTSD would be high and immediate.

451

452 **3) Setting of the Human Research**

453 This study requires three visits including an initial assessment and two testing/scanning sessions
454 separated by six-weeks of daily light exposure treatment at home.

455 For the initial assessment and the baseline testing session, subjects will be seen at the Lab of Dr.
456 [name] in the University of Arizona Department of Psychiatry. There, subjects will complete personality
457 assessments, a comprehensive cognitive assessment battery, and several tests of motor functioning.

458
459 **Magnetic Resonance Imaging (MRI) Procedures:** The data collection will occur at the research-
460 dedicated University of Arizona scanner facility that houses a new 3 Tesla magnet (see Equipment for
461 description). For functional neuroimaging, audio and visual stimulus presentation equipment is available
462 through the Resonance Technologies headphone/goggle system or high-definition MRI-compatible LCD-
463 display (viewed through a mirror in the head cage). An fMRI compatible EEG system including caps,
464 cabling, and pre-amplifier is integrated with this space (see Equipment for description). Scanner data are
465 transferred securely to a RAID storage system for subsequent transfer to PI laboratories. Offline analysis
466 will take place in the Laboratory of PI [name].

467 In January 2013, the University of Arizona purchased a Siemens Magnetom TIM Skyra 3T that is
468 capable of high-resolution imaging capabilities. This whole-body 3.0T device will be configured with 48
469 receiver channels and up to 204 integrated coil elements. It is capable of integrated parallel acquisition
470 techniques and provides higher signal to noise in the parallel imaging mode than its predecessor, the Trio.
471 The maximum acceleration factor using parallel imaging is 16 using either mSENSE or GRAPPA, and
472 3D scanning can be accelerated in two directions (maximum acceleration factor of 4 in second direction).
473 The gradients of the Skyra have a maximum amplitude of 45 mT/m and a maximum slew rate of 200 T
474 Tm⁻¹s⁻¹, yielding a minimum rise time of 225µs. The vector gradient performance (vector summation of
475 all three gradient axes) results in a maximum effective amplitude of 78 mT/m and a maximal effective
476 slew rate of 346 Tm⁻¹s⁻¹. All three gradient coils are force-compensated to reduce vibration and deliver
477 superior eddy current performance. The water cooled gradient amplifier has a maximum amplitude
478 potential of 2,250 volts and a maximum current output of 750 amps. The instrument has a minimum slice
479 thickness (in two dimensions) of 0.1 mm and a minimum partition thickness (in three dimensions) of 0.05
480 mm. The instrument produces high sensitivity, with main field, or B0, homogeneity of 1.4 ppm VRMS for
481 a 40 cm diameter spherical volume. Single shot EPI sequences for measuring diffusion-weighted data sets
482 with up to 256 directions of diffusion weighting are also a part of this instrument's capability. It provides

**FORM: Application for Human Research**

| NUMBER | FORM DATE | PAGE |
|--------|-----------|----------|
| F200 | 02/2014 | 17 of 44 |

483 diffusion tensor imaging and parametric maps derived from fractional anisotropy calculated in real time,
484 automatically. Additional sequence options include Arterial Spin Labeling, and susceptibility weighted
485 imaging (SWI) with both fully supported with parametric and phase map reconstructions.

486 All structural and functional MRI studies will be conducted in concert with the University of
487 Arizona Translational Bioimaging Resource. Subjects in this study will be studied in a scanner that has a
488 field strength of 3 Tesla. This field strength has been approved by the FDA for routine clinical use. The
489 three instruments are maintained by GE service engineers and currently meet or exceed manufacturer's
490 specifications on performance. For functional neuroimaging, audio and visual stimulus presentation
491 equipment is available through the Resonance Technologies headphone/goggle system.

492 A research area, Room 1564 (400 square feet), located immediately adjacent to the 3.0 Tesla
493 scanner, is equipped with 3 PC/Linux workstations and sgi O2 for data transfer and storage, image
494 processing, and data manipulation. All workstations are networked through a central hub and are
495 protected against external tampering using firewalls within the UAMC computer network.

496 Functional MRI is mostly done in MR3, a General Electric 3.0T HD Signa Excite scanner. It is
497 equipped with Optimized ACGD Gradients (40mT/m, 150 mT/m/ms slew rate running 12x software). It is
498 a 55cm diameter long bore magnet. This instrument is equipped with a head coil, 8 channel HR brain
499 array, a phased array neurovascular coil, 8 channel phased array spine coil, extremity coils (knee and
500 wrist) and a torso coil. MR3 has multinuclear spectroscopy capability and high order shims.

501 502 **4) Resources available to conduct the Human Research**

503 [name] effort is 100% devoted to research; he does not have clinical or teaching time
504 mandated as part of his FTE. He funds several Research Technicians and Research Assistants and one lab
505 manager.

506 The Department of Psychiatry has staff devoted to research administration, including an upper
507 level administrator and a regulatory coordinator. All have experience with IRB/regulatory matters and
508 grants administration. Business office staff is knowledgeable in grants finance and accounting, and federal
509 work-study students devoted to research are available for data entry and other administrative support.

510 [name] includes computing equipment such as backup drives and external hard drives,
511 backup surge protectors, intercom system, neuroimaging workstations with 6 TB minimum storage each;
512 Actiwatch sleep monitors watches, docks, and software analysis programs; Coulbourne Fear Conditioning
513 Suite, FaceRead + Observer XT System, sleep profiler ambulatory EEG monitoring systems, and other
514 software including EPrime, MatLab, SPSS, and Adobe Captivate.

515 The Department of Psychiatry provides personal computer resources for word processing, email
516 transmission, internet access, and simple statistical analysis for staff, in addition to laser printers, fax
517 machines, scanners and photocopy machines. In addition to these resources, the University of Arizona
518 maintains full computer and data analytic processing components available to all university faculty on a
519 fiber-optic network system, with automatic daily backup available on a secure server. There is full time
520 computer support in the Department of Psychiatry for these resources.

521 This project may use non-FDA-approved devices that are approved for use on the Translational
522 Bioimaging Resource (TBIR) MRI scanner through IRB protocol 1911166043, "Translational

**FORM: Application for Human Research**

| NUMBER | FORM DATE | PAGE |
|--------|-----------|----------|
| F200 | 02/2014 | 18 of 44 |

523 Bioimaging Resource Umbrella MRI Protocol.” TBIR, a UA Core Facility
524 (<https://ua.ilab.agilent.com/landing/3645#/about>), is housed within the UA Biosciences Research
525 Laboratory (BSRL) building.

526 All study personnel will have up to date CITI training and study protocol training from the PI or PI
527 designee.

528

529 **5) Study Population**

530 The target population is combat-exposed military personnel and other non-military individuals
531 who meet diagnostic criteria for PTSD. Participants in the study will include active duty or recently
532 discharged combat-exposed military personnel from Operation Enduring Freedom/Operation Iraqi
533 Freedom (OEF/OIF) meeting DSM-V diagnostic criteria for PTSD, in addition to some individuals from
534 the general population who meet DSM-V diagnostic criteria for PTSD to achieve a total sample size of 90
535 participants, which we anticipate will require enrolling up to 108 individuals to account for attrition. An

536 age range of 18-50 years has been selected to minimize possible developmental and degenerative
537 effects that could be expected in younger and older subjects and to encompass the age range of the
538 majority of military personnel. Participants will be recruited from several sources. Active duty
539 participants will be recruited according to the guidelines specified by the CDMRP upon award receipt.
540 The PI, a U.S. Army Reserve Research Psychologist (Lieutenant Colonel), already has a number of
541 established relationships and collaborations with leaders in the Army Medical Department (AMEDD), the
542 Pentagon, several major medical treatment facilities (MTFs), and all three of the Army’s primary research
543 laboratories, including the Walter Reed Army Institute of Research (WRAIR), the U.S. Army Institute of
544 Environmental Medicine (USARIEM), and the U.S. Army Aeromedical Research Laboratory
545 (USAARL). It is anticipated that potential recruitment of active duty, Reserve, and National Guard
546 participants will be effectively facilitated according to the guidelines specified by the CDMRP.

547 Participants will be recruited primarily from the Tucson area via IRB approved internet, newspaper, and
548 radio advertisements, and contact with individual units. Facebook advertisements and flyers will also be
549 utilized to recruit subjects, as described in greater detail below.

550

551 **Inclusion Criteria:**

- 552 1) age 18-50 years;
- 553 2) right handedness or right-hand dominance as assessed by the Edinburgh Handedness Inventory (EHS)
(necessary to avoid mixed lateralization on brain imaging);
- 554 3) SCID diagnosis consistent with PTSD

555

556 **Exclusion Criteria:**

- 558 1) History of head injury with loss of consciousness for greater than 30 minutes, or post-traumatic
559 amnesia for >24 hours, or major neurological illness (e.g. epilepsy, multiple sclerosis/MS);
- 560 2) Chronic medical (e.g. heart conditions, cystic fibrosis, diabetes, cancer, HIV/AIDS, HEP C, thyroid
561 problems, high blood sugar) or psychiatric (e.g. bipolar disorder/manic or hypomanic episodes,
562 personality disorders, schizophrenia/other psychotic disorders, severe OCD or ADHD) conditions that
563 would confound interpretation of results;

**FORM: Application for Human Research**

| NUMBER | FORM DATE | PAGE |
|--------|-----------|----------|
| F200 | 02/2014 | 19 of 44 |

564 3) Left-handedness or left-hand dominance if ambidextrous (could affect brain lateralization and add error
565 variance to scanning);
566 4) Abnormal visual acuity that cannot be corrected by contact lenses (necessary to see stimuli in the
567 magnetic environment of the scanner);
568 5) IQ estimate less than 70;
569 6) Metal within the body, pregnancy, or other contraindication for MRI procedures;
570 7) Ongoing trauma (e.g. currently being in an abusive relationship) or non-qualifying trauma (e.g. index
571 trauma emotional/verbal abuse, children being taken away by the CPS, divorce, natural deaths by age
572 or illness);
573 8) Previous formal treatment with light therapy;
574 9) History of light-induced migraine or epilepsy; medical complications that could elevate the risk of
575 discomfort associated with light-therapy;
576 10) Use of medications that could affect functional neuroimaging results (e.g., beta-blockers, mood
577 stabilizers, atypical antipsychotics, benzodiazepines, hypertension medication, chemotherapy,
578 photosensitive medications etc.). Patients currently taking other psychotropic medications (i.e.,
579 “treatment as usual”) must be stabilized for at least 4-weeks prior to participation. Although
580 participants will not be excluded from participation, detailed history and dosages will be documented
581 and examined as appropriate in statistical analyses.
582 11) Current suicidal intent based on an assessment conducted by a licensed clinical psychologist;
583 12) Currently taking or anticipating the need to take sleep-inducing medications (e.g., zolpidem) or
584 supplements that have known effects on sleep (e.g., melatonin) during the course of the study.
585 a. Patients currently taking other psychotropic medications (i.e., “treatment as usual”) must be
586 stabilized for at least 4-weeks prior to participation. Although participants will not be
587 excluded from participation, detailed history and dosages will be documented and examined as
588 appropriate in statistical analyses. Due to the broad range of sleeping disturbances that are
589 observed with PTSD and the likely difficulty in recruiting sufficient numbers of participants,
590 we will not be excluding any particular sleep disorder, but will collect data regarding these
591 sleep related problems so that it may be possible to statistically control for the effect of the
592 BLT treatment on different forms of sleep problems;
593 13) Index trauma occurring before the participant is 18 years of age;
594 14) Index trauma occurring 10 years or longer prior to participation in the study;
595 15) WRAT4 reading test score indicative of less than a 6th grade level of reading comprehension;
596 16) Drug use: Marijuana use not exclusionary. Past drug dependence (other than marijuana) not
597 exclusionary if individuals have sustained remission (no drug use in the past 12 months).

598 6) Recruitment Methods and Consenting Process

599 Please note: *The Human Research Protection Office (HRPO) with US Army Medical Research and*
600 *Materiel Command must approve any major amendment to this study prior to its implementation.*
601 *Therefore, implementation of any amendment which requires HRPO approval, including use of revised*
602 *consents, will not begin until HRPO approval is received.*

**FORM: Application for Human Research**

| NUMBER | FORM DATE | PAGE |
|--------|-----------|----------|
| F200 | 02/2014 | 20 of 44 |

604 Participants will be recruited from several sources. Active duty participants will be recruited
605 according to the guidelines specified by the Department of Defense's (DoD's) Congressionally Directed
606 Medical Research Programs (CDMRP) upon award receipt. The PI, a U.S. Army Reserve Research
607 Psychologist (Lieutenant Colonel), already has a number of established relationships and collaborations
608 with leaders in the Army Medical Department (AMEDD), the Pentagon, several major medical treatment
609 facilities (MTFs), and all three of the Army's primary research laboratories, including the Walter Reed
610 Army Institute of Research (WRAIR), the U.S. Army Institute of Environmental Medicine (USARIEM),
611 and the U.S. Army Aeromedical Research Laboratory (USAARL). It is anticipated that recruitment of
612 active duty, Reserve, and National Guard participants will be effectively facilitated and will proceed
613 according to the guidelines specified by the CDMRP. Civilian veterans, Reserve Soldiers, National
614 Guard Soldiers, and nonmilitary combat-exposed civilians will also be recruited primarily from the local
615 Tucson and surrounding area, from clinical programs within the Department of Psychiatry, and local
616 events and advertisements on the web (including our own websites, appropriate sections of community
617 websites and forums [e.g. Craigslist], Facebook or other social media, and reputable clinical trial referral
618 websites [e.g. StudyKik], and similar websites). Our lab will post IRB approved advertising text on
619 similarly themed Facebook groups, which allow for outside posts of this nature. We will adhere to any
620 page specific posting requirements as well as Facebook Terms of Service for appropriate behavior. We
621 may also utilize print, radio advertisements, TV, and UAHS and College of Medicine hallway and lobby
622 monitors and flyers on campus, as well as UA list serves such as 3D memos etc. (ad text will be IRB
623 approved), Residence Halls, and other UA buildings (with the appropriate recruitment site authorization
624 obtained prior).

625 We will make approved screening surveys (e.g., *Recruitment Survey.pdf*) available on UA
626 departmental (e.g., Department of Psychiatry, Department of Psychology) or other UA-affiliated websites
627 (e.g., UAHS Clinical Research Studies website), as well as other online media appropriate for research
628 advertising such as clinical trial referral websites, survey websites (e.g., Qualtrics, Survey Monkey),
629 research data management (e.g., REDCap), and crowdsourcing websites (e.g., Amazon Mechanical Turk
630 [MTurk]). Crowd-sourcing platforms facilitate recruitment of and payment to individuals for their
631 participation in online surveys. When disseminated via this method, our surveys will be restricted to
632 participants who live in Arizona and will be securely hosted in Qualtrics, REDCap, or other such
633 reputable survey-host.

634 In addition, UA Clinics (i.e. CAPS, Campus Health, etc.), and outside clinics/businesses in the
635 greater Tucson area will be utilized to refer patients to the study. Treating physicians at clinics may be
636 informed of the study and the inclusion/exclusion criteria, if they feel they have a patient who qualifies
637 they will provide the patient with a study recruitment flyer and the patient will contact our office if they
638 are interested. Recruitment site authorization will be obtained prior to recruitment occurring at any site;
639 this documentation will be kept within our research files. A trained research assistant will initially screen
640 individuals who respond to these advertisements via telephone interview. Individuals meeting basic
641 eligibility requirements will be scheduled for an intake visit. Participants whose intake visits are
642 scheduled more than six weeks after the date of the initial phone screen will be given a shortened follow-
643 up phone screen prior to the intake visit, in order to ensure that no changes have taken place which may
644 affect their eligibility. Recruitment and advertisement materials will include brief descriptions of the

FORM: Application for Human Research

| NUMBER | FORM DATE | PAGE |
|--------|-----------|----------|
| F200 | 02/2014 | 21 of 44 |

645 purpose of the study, the general procedures of the study, important inclusion and exclusion criteria, the
646 amount of compensation, and the phone number or email address to contact if interested.

647 To encourage full participation and minimal subject discontinuation, subject compensation will
648 follow the prorated schedule as seen in Section 12.

649
650 Subjects will be made aware via the Informed Consent Form that if they are active duty military
651 personnel, they are not eligible to receive compensation for time spent completing assessments unless
652 they are on official military leave status in accordance with Title 24 United States Code 30. Therefore,
653 any active duty military personnel not on leave status will not receive compensation for time spent
654 completing assessments as attested to by all subjects as part of the informed consent process.
655 We will request that subjects attest to their understanding of this by initialing the following:
656

657 *Participants who are active duty cannot be compensated for any of the research activities while they
658 are “on-duty”. It will be the volunteer’s responsibility to ensure they have taken leave and obtained
659 the right permissions, if required, in order to receive compensation for this study.*

660 _____ Please initial to indicate you acknowledge this requirement.

661
662 **If you are active duty military personnel**, you are not eligible to receive compensation for time
663 spent completing assessments while you are “on duty.” In accordance with Title 24 United States
664 Code 30, active duty military personnel must be on leave status during each of the three assessment
665 sessions in order to be compensated. If you are on active duty, **it is your responsibility** to ensure that
666 you have completed the appropriate paperwork for leave and obtained the necessary permissions to
667 allow you to participate in this study. If you are on leave status, you will be compensated for the 3
668 assessment sessions according to the schedule listed above.

669 **Screening Procedures:**

670 Potential subjects will be screened over the phone by a clinically trained research assistant to
671 verify that subjects meet all inclusion criteria and do not meet any of the exclusionary criteria.
672 Information collected during screening will not be used as a part of the research data. Subjects who meet
673 basic eligibility requirements will be scheduled for an intake visit. Informed consent will be obtained prior
674 to initiating any further screening procedures. After informed consent has been determined, a supervised
675 Research Technician who has been trained and meets predetermined qualifications to administer a
676 Structured Clinical Interview by doctoral level clinical psychologists with training and experience
677 administering these instruments will conduct a structured clinical interview to screen for any psychiatric
678 diagnoses. Once eligibility for the study has been confirmed or rejected, the subject will be placed into the
679 appropriate experimental group, or excluded from the study if any information yielded from this visit is
680 consistent with the exclusionary criteria.

681

682 **Informed Consent Process:**

683 • Either the PI or a trained research assistant will be responsible for explaining the study, answering
684 questions, and obtaining written informed consent from participants.

**FORM: Application for Human Research**

| NUMBER | FORM DATE | PAGE |
|--------|-----------|----------|
| F200 | 02/2014 | 22 of 44 |

- Initial description of the study will be provided during the telephone screening process. The actual consent process will occur during the in-person intake visit. The consent process is the first part of the visit, and will take place in a private office. The participant will have the opportunity to read the consent form, and each section will be explained in detail by the research assistant. The participant will have a chance to ask questions and have them answered fully before making a decision to participate. All volunteers will receive a copy of the signed consent form once they and the study staff member obtaining consent have signed the form.
- Only adult participants with normal intellectual capacity (IQ≥70) will be included in the study. Any evidence of altered mental status or capacity, due to substances, medications, cognitive status, or injury will result in discontinuation of the consent process.
- Participants will be consented in a private office, but may be accompanied by anyone of their choosing. There will be no time pressure and potential volunteers may discuss possible participation with anyone and may choose to suspend the consent process and return on another occasion, as long as they have not been disqualified or the study has terminated.
- Participants will be monitored closely by study staff and queried about continued participation after completion of each major component of the study (i.e., neurocognitive testing, functional imaging, sleep study, etc.) and if there are visible signs that the participant may be having difficulty tolerating the procedures.
- We will not enroll subjects who cannot provide written informed consent; therefore plans to consent the subject's Legally Authorized Representative are not applicable.
- Because the study requires the ability to read many self-report instruments and complete several written tasks, we will not be enrolling anyone that cannot read with at least 6th grade proficiency, as indicated by the WRAT 4 Reading test. Because the study requires the ability to comprehend a variety of self-report instruments that are only available in English, we will not be enrolling participants whose primary language is not English. No waiver of consent is being sought for this study.
- All participants will be adults (age 18 to 50), thus issues regarding assent from minors are not relevant.

7) Procedures involved in the Human Research

General Procedure: Over a 4-year period, 108 participants between the ages of 18 and 50 will be recruited to participate (to reach a final n of 90 subjects, assuming 20% attrition). Participants will comprise active duty, Reserve, National Guard, or recently discharged combat-exposed military personnel or DoD contractors from Operation Enduring Freedom/Operation Iraqi Freedom (OEF/OIF) meeting DSM-V diagnostic criteria for PTSD, in addition to some non-military individuals who meet the DSM-V diagnostic criteria for PTSD. Combat-exposed individuals within 10 years of return from OIF/OEF will be eligible. An age range of 18-50 years has been selected to minimize possible developmental and degenerative effects that could be expected in younger and older subjects and to encompass the age range of the majority of military personnel.

FORM: Application for Human Research
NUMBER
FORM DATE
PAGE

F200

02/2014

23 of 44

724 Prior to data analysis, subjects who consent will have a follow-up phone call where they will be
 725 administered the PCL-5, PHQ-9, and be asked about general sleep problems using the ESS and ISI.
 726

727 The procedures will essentially be identical to those used successfully in our pilot study of patients
 728 with mTBI. Participants will attend three laboratory sessions (see Figure 10 below). Visit 1 involves
 729 informed consent, demographic data collection, and basic psychiatric assessment. Participants will be
 730 provided with a wrist actigraph sleep monitor. After a week of at home monitoring, each participant will
 731 return for Visit 2, which is involves comprehensive neurocognitive assessment, neuroimaging, fear
 732 conditioning testing, objective sleepiness monitoring and heart rate monitoring. Then participants will be
 733 randomly assigned to one of two light therapy conditions (n = 45 per group) differing only in the
 734 wavelength emitted by each light therapy device. Participants will be randomly assigned to either the BL
 735 condition or the PL condition, using computerized permuted block randomization to match groups by
 736 gender. Participants assigned to the active treatment condition will undergo 6-weeks of at-home treatment
 737 with a light device fitted with blue light (BL) diodes, while those assigned to the Placebo (PL) condition
 738 will undergo 6-weeks of identical treatment with a device fitted with amber light diodes. To objectively
 739 monitor sleep, participants will wear a wrist actigraph for the duration of the study. During the 6 weeks
 740 of treatment, participants will use the light device for 30-minutes each morning, within 2-hours of
 741 awakening (verified via light sensor built into the wrist actigraph, daily time stamped electronic sleep
 742 diary, and compliance as measured by wattage usage/time meter). After 6-weeks, participants return for
 743 Visit 3 and undergo a follow-up neurocognitive assessment, neuroimaging, fear conditioning, objective
 744 sleepiness monitoring, and heart rate monitoring. These procedures have been extremely successful and
 well tolerated in our pilot study.

[figure not shown]

Figure 10. Study Design: Participants attend 3 separate sessions. Visit 1 is simply an intake session that includes consent forms and SCID assessment. Visit 2 and 3 are identical, and include a comprehensive neurocognitive test battery, and neuroimaging. Visit 2 and 3 are separated by a 6-week treatment period with either Blue Light Therapy or Amber Placebo Light Treatment.

745
 746 **Subject Screening:** Participants whose intake visits are scheduled more than six weeks after the date of
 747 the initial phone screen will be given a shortened follow-up phone screen prior to the intake visit, in order
 748 to ensure that no changes have taken place which may affect their eligibility.
 749

Intake Visit (Visit 1): Participants will be given a full description of the study, have the opportunity to
 750 ask questions, and will provide written informed consent, and will be evaluated for PTSD severity using
 751 the Structured Clinical Interview for DSM-V (SCID). The Morningness Eveningness Questionnaire
 752 (MEQ) will be administered to assess circadian rhythm disturbances prior to light treatment. The combat
 753 exposure scale (CES) will also be administered to participants with combat-related PTSD to inform us of
 754 the extent and nature of combat exposure in military participants. The Weschler Abbreviated Scale of
 755 Intelligence (WASI-II) will be administered to control for variation in intelligence levels amongst
 756 participants. The AUDIT and MUSE questionnaires will also be given to determine the degree and extent
 757 of alcohol and marijuana use, though neither of these scales will be utilized as a means to determine

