1061 considered as falling into three types: 1) missing completely at random, 2) missing at random, or 3)
1062 missing not at random. The type of missing data will dictate the approach. Assuming type 1, and that the
1063 number of missing values is low, we will use a standard listwise deletion procedure. However, assuming
1064 that a larger number of values is missing, and data are not missing completely at random, we will be able
1065 to apply missing data imputation methods.

1066 **Power Analysis:** A power analysis based on a proposed sample size of 90 subjects suggested that
1067 with an omnibus 2 between-groups (BL vs. PL) x 2 within-subjects (pre- vs post-treatment) mixed design,
1068 assuming a moderate effect size ($f = .25$), and $\alpha = .05$, there should provide be adequate power to detect
1069 most effects. First, the primary hypotheses of the study focus on interaction effects across groups (i.e.,
1070 treatment x session interactions), which will have exceptional power ($1-\beta = 0.99$) to detect a moderate
1071 effect size at $\alpha = .05$ (see Figure 18A). Paired comparisons within each group of will also have excellent
1072 power of .91 to detect moderate effect size changes ($d = .50$), with 2-tailed tests (see Figure 18B).
1073 Without regard to group differences, a sample size of 90 would yield power = 0.84 to detect a moderate
1074 linear association (i.e., $r \geq .30$) between a predictor variable (e.g., average sleep; change in sleep
1075 parameters, PTSD symptom severity; neurocognitive performance; etc.) and an outcome variable (e.g.,
1076 fMRI signal intensity changes; spectroscopic metabolite changes; etc.), with a two-tailed test at $\alpha = .05$
1077 (see Figure 16). Thus, the proposed sample size of $n = 45$ per group appears to provide adequate power
1078 for testing the major hypotheses of the proposed study.

FORM: Application for Human Research

| NUMBER | FORM DATE | PAGE |
|---------------|------------------|-------------|
| F200 | 02/2014 | 32 of 44 |

1079 **Functional Image Pre-Processing:** Functional neuroimaging data will be preprocessed in SPM8
1080 [123]. Following standard algorithms, functional images will be slice-time corrected, co-registered to
1081 their anatomical T1-weighted images, realigned, unwarped to correct for field inhomogeneity, normalized
1082 to the standard three-dimensional space of the Montreal Neurological Institute (MNI), spatially smoothed

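### Recruiting 108 with 20% attrition leaves 86 completers, not the 90 on which every power figure rests; 108 to 90 is 16.7% attrition

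*Combined protocol and SAP*

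**What the plan says.** Section 7, General Procedure, says that "108 participants between the ages of 18 and 50 will be recruited to participate", with the purpose in brackets: "to reach a final n of 90 subjects, assuming 20% attrition". Later in the same section, participants are "randomly assigned to one of two light therapy conditions (n = 45 per group").

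Section 5, Study Population, gives the same pair of numbers without a percentage. It sets a total of 90 "participants, which we anticipate will require enrolling up to 108 individuals to account for attrition".

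The Power Analysis in part D, Data Analysis, takes 90 subjects (45 per group) as its basis throughout:

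- 0.99 for the treatment by session interaction at f = .25 and a significance level of .05;
- for comparisons within a group, "power of .91 to detect moderate effect size changes ($d = .50$), with 2-tailed tests";
- for linear association, "a sample size of 90 would yield power = 0.84 to detect a moderate" correlation of .30 or more.

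**The concern.** Attrition is ordinarily the share of those enrolled who are lost, and the sentence offers no other definition. On that reading the head count, the loss rate and the final number in one sentence contradict each other, and nothing elsewhere in the document reconciles them.

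The final number is the one that carries weight, because all the stated powers are computed at 90. If 20% is the real planning assumption, 108 recruits do not deliver 90 completers. If 90 completers from 108 is the real expectation, the stated attrition rate is wrong. The data analysis section plans listwise deletion when few values are missing and they are missing completely at random, so the number of completers can become the number analysed.

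**Working it through.** **Inputs.** From section 7: 108 recruited, 90 final, 20% attrition, 45 per group. From the Power Analysis: N = 90, f = .25, d = .50 (paired), r = .30, two-sided .05, and stated powers of 0.99, .91 and 0.84. The text gives no pre/post correlation (rho), so values of .4 and .5 are assumed for the interaction.

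**Step 1: the recruitment arithmetic.**

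- Completers from 108 at 20% attrition: 108 x (1 - 0.20) = 86.4, about 86, or 43 per arm if losses are equal.
- Recruits needed for 90 at 20% attrition: 90 / (1 - 0.20) = 112.5, so 113.
- Attrition implied by 108 and 90: (108 - 90) / 108 = 18 / 108 = 16.7%.
- Origin of 108: 90 x 1.20 = 108. The 18 extra participants are 20% of 90 but 16.7% of 108.

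**Step 2: reproduce the stated powers at 90.**

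- Paired comparison, n = 45, noncentral t with 44 df and noncentrality 0.50 x sqrt(45) = 3.354: power 0.907. Stated .91, reproduced.
- Correlation, N = 90, noncentral t with 88 df and noncentrality [0.30 / sqrt(1 - 0.09)] x sqrt(90) = 2.983: power 0.839. Stated 0.84, reproduced.
- Interaction, noncentral F with 1 and 88 df and lambda = f² x N x 2 / (1 - rho) = 0.0625 x 90 x 2 / (1 - rho). At rho = .4, lambda = 18.75 and power is 0.990. At rho = .5, lambda = 22.5 and power is 0.997. The stated 0.99 is reproduced.

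**Step 3: repeat at 86 (43 per arm).**

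| Quantity | Stated | Computed at 90 | Computed at 86 |
|---|---|---|---|
| Paired, d = .50 | .91 | 0.907 | 0.893 |
| Correlation, r = .30 | 0.84 | 0.839 | 0.822 |
| Interaction, f = .25, rho .4 | 0.99 | 0.990 | 0.987 |
| Interaction, f = .25, rho .5 | 0.99 | 0.997 | 0.996 |

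The noncentralities at 86 are 0.50 x sqrt(43) = 3.279 for the paired test and 0.3145 x sqrt(86) = 2.916 for the correlation. For the interaction, lambda is 10.75 / 0.6 = 17.92 at rho .4 and 10.75 / 0.5 = 21.5 at rho .5.

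The largest loss is 0.839 - 0.822 = 0.017 for the correlation. In rounded figures the paired power goes from .91 to 0.89 and the correlation power from 0.84 to 0.82.

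**The case against.** The best defence is that this is one loosely worded percentage. Because 108 is 90 x 1.2, the 20% can be read as a margin added to the target, and section 5 gives 108 as an upper limit with no rate at all. On that reading the head counts are right and no conclusion of the plan changes. Much of this stands: it is the likeliest explanation of the slip, and it is why the point is minor. It does not rescue the sentence, which calls the 20% attrition.

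A second objection is that changing 20% to 16.7% merely fits the assumption to the head count. That also stands, so the correction should follow the attrition that the sponsor actually expects. Recruiting 113, which keeps both 20% and 90, should be named among the possibilities.

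A reader might go further and infer that the 0.99 for the interaction is itself wrong. Because the Power Analysis calls both f = .25 and d = .50 moderate, the reader might also take 0.99 as power for a between-arm difference of 0.50 SD of change. The documents do not support either reading. The 0.99 reproduces at plausible correlations. The text labels f and d separately and never claims 0.99 for a 0.50 SD difference between arms. The correlation used may be given in Figure 18A, which the text cites but which is not shown in the copy reviewed.

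**Conclusion.** The sentence in section 7 is wrong as written: 108 recruited, 20% attrition and 90 final are incompatible. The arithmetic needs only the usual meaning of attrition as a share of those enrolled.

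The size is minor: four fewer completers (86 against 90) and at most about 2 percentage points of power. The power figures at 86 assume equal losses in the two arms and an analysed number equal to the number of completers. The interaction figures also depend on assumed correlations of .4 to .5.

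It would be too strong to conclude that the trial is underpowered. Every recomputed power stays above 0.80 at the effect sizes that the plan itself chose.

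**What to change.** Choose according to the attrition that the sponsor really expects.

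- **If it is 16.7%:** in section 7, General Procedure, replace the 20% by *16.7% attrition (20% over-recruitment on 90)*. All power figures stay as they are.
- **If it is 20% and 108 is kept:** restate expected completers as 86 (43 per arm) in section 5, section 7 and the Power Analysis. Give paired power as 0.89, power for r = .30 as 0.82, and interaction power at f = .25 as about 0.987 to 0.996 for assumed pre/post correlations of .4 to .5.

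For information, keeping both 20% and 90 would mean recruiting 113 (113 x 0.80 = 90.4). This correction does not require it.

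The cost of either wording change is one percentage, or one completer count with its power figures. No endpoint, analysis or enrolment target changes.
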